**Key to abbreviations:**

ACEI – Angiotensin converting enzyme inhibitor; BP – blood pressure; bpm – beats per minute; HR – heart rate; ICU – intensive care unit; q – every; prn – as required; µg/Kg/min – micrograms per kilogram per minute; µg/min – micrograms per minute.

## Appendix 1B - BP management protocol for centres WITH labetalol

Early intensive BP lowering group	TREATMENT PROTOCOL
INITIAL therapy	
BP Target	SBP 130-140 mmHg reached within 60 minutes of Randomisation into the BP arm
Monitoring	
 
• Continuous HR monitoring
 
• Record BP/HR q 5 mins during active treatment, then q 15 min for first hour, q 30 min for next 5 hours and then hourly to 24 h
 

Labetalol (IV)	
 
• Labetalol test dose: 10 mg IV bolus over 1 minute
 
• If SBP > 140 mmHg and HR > 55 bpm, repeat 10 mg bolus in 5 minutes.
 
• 20 mg IV push q 5 mins until target SBP reached (< 140mmHg) or HR <55 bpm; increase to 40 mg bolus if required
 
• Maximum labetalol dose: 300 mg / 24 hours
 

Hydralazine (IV)	If BP persistently > 140 mmHg: 
 
• ADD Hydralazine with a test dose: 5 mg IV bolus over 1 minute
 
• If SBP > 140 mmHg, repeat 5 mg IV bolus in 5 minutes
 
• If SBP still >140mmHg, give 10 mg IV bolus q 5 mins until target SBP reached. Increase to 20 mg bolus if required
 
• Maximum hydralazine dose = 240mg/24 hours
 

Glyceryl Trinitrate (Topical)	If BP persistently > 140 mmHg: 
 
• ADD topical glyceryl trinitrate (paste or patch) at a rate of 5-10 mg/24hour (≈200-400 µg/hour). NB: also known as topical nitroglycerin
 

Continuous IV Infusions (requires ICU admission)	If BP persistently > 140 mmHg: 
 
• Labetalol infusion 2-8 mg/min to a maximum of 300 mg/24 hours (consider this if response to labetalol boluses is adequate but brief)
 
• If target still not reached, ADD infusion of hydralazine 50-150 µg/min OR glyceryl trinitrate 1-100 µg /min
 
• OR start infusion of Nicardipine 5-15 mg/hour
 

MAINTENANCE therapy	
BP Target	Maintenance of SBP 130-140 mmHg
Monitoring	Once SBP is under target (confirmed by 4 readings 15 minutes apart): 
 
• Record BP/HR q 30 minutes for 5 hours and then q 1 h for 18 h
 

IV treatment prn	If SBP exceeds 140mmHg at any point: 
 
• Give Labetalol (20-40 mg) and/or hydralazine (10-20 mg) boluses. BP and HR should then be recorded 5 and 15 minutes later
 
• If SBP is <140mmHg, Labetalol 10-40 mg (dose dependent on initial response) should be administered q 6 hours for the first 24 hours after symptom onset (total of 3 doses)
 
• If SBP < 130 mmHg or HR < 55 bpm, then cease treatment.
 

- Maximum labetalol dose: 300 mg/24 hours
- **Note: labetalol and hydralazine may be used together during the maintenance phase**

*Oral treatment*

Start treatment by 24 hours (use nasogastric if required).

- If not contraindicated and no other drug is specifically indicated, start combination therapy of ACEI + diuretics in addition to previous anti-hypertensives

**Note: Monoamine oxidase inhibitors are not recommended with labetalol. Phosphodiesterase inhibitors must not be used with GTN.**

**Key to abbreviations:** ACEI – Angiotensin converting enzyme inhibitor; BP – blood pressure; bpm – beats per minute; HR – heart rate; ICU – intensive care unit; q – every; prn – as required;  $\mu\text{g}/\text{Kg}/\text{min}$  – micrograms per kilogram per minute;  $\mu\text{g}/\text{min}$  – micrograms per minute.

## Appendix 1C - BP protocol for centres with Urapidil (China)

Early intensive BP lowering group	TREATMENT PROTOCOL
INITIAL therapy	
BP Target	SBP 130-140 mmHg reached within 60 minutes of Randomisation into the BP arm
Monitoring	
 
• Continuous HR monitoring
 
• Record BP/HR q 5 mins during active treatment, then q 15 min for first hour, q 30 min for next 5 hours and then hourly to 24 h
 

Urapidil (IV)	
 
• Urapidil test dose: 5 mg IV bolus over 1 minute
 
• If SBP > 140 mmHg and HR >55 bpm, repeat 5 mg bolus in 5 minutes
 
• 10-25 mg IV push q 5 mins until target SBP reached (< 140mmHg) or HR <55 bpm
 
• If HR increases by >15 bpm or is >90 bpm, add IV beta blocker
 

Hydralazine (IV)	If BP persistently >140 mmHg: 
 
• ADD Hydralazine with a test dose: 5 mg IV bolus over 1 minute
 
• If SBP > 140 mmHg, repeat 5 mg IV bolus in 5 minutes
 
• If SBP still > 140mmHg, give 10 mg IV bolus q 5 mins until target SBP reached. Increase to 20 mg bolus if required
 
• Maximum hydralazine dose = 240mg/24 hours
 

Glyceryl Trinitrate (Topical)	If BP persistently > 140 mmHg: 
 
• ADD topical glyceryl trinitrate (paste or patch) at a rate of 5-10 mg/24hour (≈200-400 µg/hour). NB: also known as topical nitroglycerin
 

Continuous IV Infusions (requires ICU admission)	If BP persistently >140 mmHg: NB: It is recognized that many sites will proceed directly to urapidil infusion following an initial bolus. 
 
• Urapidil infusion 5-30 mg/hour
 
• If target still not reached, ADD infusion of hydralazine 50-150 µg/min OR glyceryl trinitrate 1-100 µg/min
 

MAINTENANCE therapy	
BP Target	Maintenance of SBP 130-140 mmHg
Monitoring	Once SBP is under target (confirmed by 4 readings 15 minutes apart): 
 
• Record BP/HR q 30 minutes for 5 hours and then q 1 h for 18 h.
 

IV treatment prn	If SBP exceeds 140mmHg at any point: 
 
• Give Urapidil (10-25 mg) and/or hydralazine (10-20 mg) boluses. BP and HR should then be recorded 5 and 15 minutes later
 
• If SBP is <140mmHg, Urapidil 10-25 mg (dose dependent on initial response) should be administered q 6 hours for the first 24 hours after symptom onset (total of 3 doses)
 

	
 
• If SBP < 130 mmHg or HR < 55 bpm, then cease treatment
 
• If HR increases by >15 bpm or is >90 bpm, add IV beta blocker
 
• Note: urapidil and hydralazine may be used together during the maintenance phase
 

Oral treatment	
Start treatment by 24 hours (use nasogastric if required)
 
 
• If not contraindicated and no other drug is specifically indicated, start combination therapy of ACEI + diuretics in addition to previous anti-hypertensives
 

**Note: Monoamine oxidase inhibitors are not recommended with this BP lowering agent and phosphodiesterase inhibitors must not be used with GTN.**

**Key to abbreviations:** ACEI – Angiotensin converting enzyme inhibitor; BP – blood pressure; bpm – beats per minute; HR – heart rate; ICU – intensive care unit; q – every; prn – as required; µg/Kg/min – micrograms per kilogram per minute; µg/min – micrograms per minute.

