### **6.1 BP control arm**

#### *6.1.1 Early Intensive BP Lowering Group*

The aim is to achieve a systolic BP level 130-140 mmHg **within 60 minutes** of Randomisation into the BP arm *and* to maintain this BP level for the next 72 hours (or until hospital discharge or death if this should occur earlier). A standardised i.v. BP lowering regimen using locally available and approved i.v. BP lowering agents will be used, commenced in the emergency department and later in a high dependency area (e.g. acute stroke or neurointensive care unit) as is usual for patients receiving rtPA.

BP lowering will be titrated by repeat i.v. bolus or infusion, with a systolic BP of <130 mmHg being the safety threshold for cessation of therapy. It is anticipated that i.v. agents will be required for at least the first several hours in most cases but the timing of switch to oral BP lowering agents will be at the discretion of the responsible clinician according to BP control and patient status. It is also expected that i.v. therapy will continue to be required during the initiation of oral anti-hypertensive therapy, to maintain the systolic BP levels 130-140 mmHg.

When administering BP lowering treatment, care is required to ensure that severe hypotension is avoided in patients by checking first for potential dehydration and providing intravenous fluids.

Since the study seeks to address the impact of BP lowering and not a specific agent, and to ensure the trial result is maximally generalisable to existing routine practice, some flexibility is allowed in the use of locally available i.v. agents (e.g. urapidil, labetalol, hydralazine, metoprolol, clevidipine), but all other aspects treatment are standardised across sites. Patients on prior oral BP lowering agents should have this continued if possible and antihypertensive therapy prescribed when patients are clinically stable as per guidelines for secondary stroke prevention. Investigators are encouraged to adhere to study protocols, provide active care, but are free to modify a patient's treatment as required according to clinical judgment.

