IV treatment prn	If SBP exceeds 140mmHg at any point: 
 
• Give Phentolamine (5 mg) and/or hydralazine (10-20 mg) boluses. BP and HR should then be recorded 5 and 15 minutes later
 
• If SBP is <140mmHg, Phentolamine 5 mg (dose dependent on initial response) should be administered q 6 hours for the first 24 hours after symptom onset (total of 3 doses)
 
• If SBP < 130 mmHg or HR <55 bpm, then cease treatment
 
• If HR increases by >15 bpm or is >90 bpm, add IV beta
 

	
blocker
 
 
Note: phentolamine and hydralazine may be used together during the maintenance phase
 

Oral treatment	
Start treatment by 24 hours (use nasogastric if required)
 
 
If not contraindicated and no other drug is specifically indicated, start combination therapy of ACEI + diuretics in addition to previous anti-hypertensives
 

**Note: Monoamine oxidase inhibitors are not recommended with this BP lowering agent and phosphodiesterase inhibitors must not be used with GTN.**

**Key to abbreviations:** ACEI – Angiotensin converting enzyme inhibitor; BP – blood pressure; bpm – beats per minute; HR – heart rate; ICU – intensive care unit; q – every; prn – as required;  $\mu\text{g}/\text{Kg}/\text{min}$  – micrograms per kilogram per minute;  $\mu\text{g}/\text{min}$  – micrograms per minute.

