## Appendix 1F- BP protocol for centres with Clevidipine

Early intensive BP lowering group	TREATMENT PROTOCOL
INITIAL therapy	
BP Target	SBP 130-140 mmHg reached within 60 minutes of Randomisation into the BP arm
Monitoring	
 
• Continuous HR monitoring
 
• Record BP/HR q 2 mins during active treatment, then q 15 min for first hour, q 30 min for next 5 hours and then hourly to 24 h
 

Clevidipine (Continuous IV Infusion) (requires ICU admission)	
 
• Clevidipine initiation dose: 2 mg/hour continuous IV for the first 1.5minuts
 
• If SBP >140 mmHg, DOUBLE the dose every 2-10 minutes (4, 8, 16 and then 32 mg/hour)
 
• Maximum dose = 32.0mg/hour
 

Hydralazine (IV)	If BP persistently >140 mmHg: 
 
• ADD Hydralazine with a test dose: 5 mg IV bolus over 1 minute
 
• If SBP >140 mmHg, repeat 5 mg IV bolus in 5 minutes
 
• If SBP still > 140mmHg, give 10 mg IV bolus q 5 mins until target SBP reached. Increase to 20 mg bolus if required
 
• Maximum hydralazine dose = 240mg/24 hours
 

Glyceryl Trinitrate (Topical)	If BP persistently >140 mmHg: 
 
• ADD topical glyceryl trinitrate (paste or patch) at a rate of 5-10 mg/24hour (≈200-400 µg/hour). NB: also known as topical nitroglycerin
 

Continuous IV Infusions (requires ICU admission)	If BP persistently >140 mmHg: 
 
• ADD infusion of hydralazine 50-150 µg/min OR glyceryl trinitrate 1-100 µg /min
 

MAINTENANCE therapy	
BP Target	Maintenance of SBP 130-140 mmHg
Monitoring	Once SBP is under target (confirmed by 4 readings 15 minutes apart): 
 
• Record BP/HR q 30 minutes for 5 hours and then q 1 h for 18 h.
 

Continuous IV treatment prn	If SBP exceeds 140mmHg at any point: 
 
• DOUBLE the dose of Clevidipine every 2-10 minutes (4, 8, 16 and then maximum dose of 32 mg/hour)
 
• If SBP is <140mmHg, Keep the dose of Clevidipine
 
• If SBP < 130 mmHg or HR < 55 bpm, then HALVE the dose of Clevidipine every 2-10 minutes and then cease treatment
 
• If HR increases by >15 bpm or is >90 bpm, add IV beta blocker
 

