Continuous IV treatment prn	If SBP exceeds 140mmHg at any point: 
 
• INCREASE the dose of Nicardipine by 2.5 mg/hour every 15 minutes (7.5, 10, 12.5 and then 15 mg/hour)
 
• If SBP is <140mmHg, Keep the dose of Nicardipine
 
• If SBP < 130 mmHg or HR < 55 bpm, then DECREASE the dose of Nicardipine by 2.5mg/hour every 2-15 minutes and then cease treatment
 
• If HR increases by >15 bpm or is >90 bpm, add IV beta blocker
 

---

*Oral treatment*

Start treatment by 24 hours (use nasogastric if required)

- If not contraindicated and no other drug is specifically indicated, start combination therapy of ACEI + diuretics in addition to previous anti-hypertensives

**Note: Monoamine oxidase inhibitors are not recommended with this BP lowering agent and phosphodiesterase inhibitors must not be used with GTN.**

**Key to abbreviations:** ACEI – Angiotensin converting enzyme inhibitor; BP – blood pressure; bpm – beats per minute; HR – heart rate; ICU – intensive care unit; q – every; prn – as required; mg/hour – milligram per hour;  $\mu\text{g}/\text{Kg}/\text{min}$  – micrograms per kilogram per minute;  $\mu\text{g}/\text{min}$  – micrograms per minute.

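### Four maintenance tables order an IV beta blocker on heart rate alone, directly after an instruction to stop or taper treatment below SBP 130 mmHg

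*Protocol*

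**What the plan says.** Protocol section 6.1.1 sets one limit for the whole intensive arm: i.v. treatment is titrated "with a systolic BP of <130 mmHg being the safety threshold for cessation of therapy". It adds that "care is required to ensure that severe hypotension is avoided in patients", by checking for dehydration and giving fluids. Its examples of locally available i.v. BP-lowering agents ("e.g. urapidil, labetalol, hydralazine, metoprolol, clevidipine") include two beta blockers, labetalol and metoprolol.

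The appendices turn this into bedside tables. Below SBP 130 mmHg the maintenance rows say:

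- Appendix 1C (urapidil): "If SBP < 130 mmHg or HR < 55 bpm, then cease treatment"
- Appendix 1D (phentolamine): "If SBP < 130 mmHg or HR <55 bpm, then cease treatment"
- Appendix 1F (clevidipine): "then HALVE the dose of Clevidipine every 2-10 minutes and then cease treatment"
- Appendix 1G (nicardipine): "then DECREASE the dose of Nicardipine by 2.5mg/hour every 2-15 minutes and then cease treatment"

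In each of these four rows the next instruction on titration is "If HR increases by >15 bpm or is >90 bpm, add IV beta blocker". The same bullet also closes the urapidil row of the initial phase in 1C and the phentolamine row of the initial phase in 1D.

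**The concern.** The bullet depends on heart rate only. When SBP is below 130 mmHg and the heart-rate trigger is also met, one line tells the site to withdraw BP-lowering treatment and the next tells it to give another drug, of a class the protocol itself uses to lower BP. A site that follows the second line literally adds such a drug below the trial's own stop threshold.

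The protocol's safety case makes this range important. Background section 6 argues that the risks of BP lowering appear only at systolic levels under 130 mmHg, and presents that range as lying outside what the protocol prescribes.

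**Working it through.** No sample size, alpha or power figure is involved. The check sets the tables side by side.

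**1. Where the bullet stands.** Seven appendices give a full regimen with an initial and a maintenance phase.

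| Appendix | Bullet in initial phase | Bullet in maintenance phase | Maintenance action below SBP 130 mmHg |
|---|---|---|---|
| 1A | no | no | cease |
| 1B | no | no | cease |
| 1C | yes | yes | cease |
| 1D | yes | yes | cease |
| 1F | no | yes | halve repeatedly, then cease |
| 1G | no | yes | step down, then cease |
| 1H | no | no | cease |

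The bullet appears in 2 of 7 initial phases and 4 of 7 maintenance phases, so in 2 + 4 = 6 of 14. None of the six carries its own systolic condition.

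**2. Does the lead-in limit it?** The maintenance rows open with a condition that SBP exceeds 140 mmHg. That cannot govern every bullet beneath it, because other bullets in the same row act at SBP below 140 and below 130 mmHg.

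**3. Can both triggers be met?** The overlap is SBP <130 mmHg together with HR >90 bpm or a rise of more than 15 bpm. SBP 125 mmHg with HR going from 60 to 76 bpm (76 − 60 = 16) qualifies. The other stop trigger, HR <55 bpm, hardly matters here: a rise of more than 15 bpm that ends below 55 needs a starting rate under 55 − 15 = 40 bpm.

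**4. Is the added drug BP-lowering in the protocol's own terms?** Yes. Section 6.1.1 names labetalol and metoprolol. Appendix 1E offers esmolol as a further BP-lowering option for sites in China, where 1C and 1D apply. Where Appendix 1A uses i.v. metoprolol, it requires BP to be persistently above 140 mmHg and sets a heart-rate floor of 55 bpm.

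**5. Which places are exposed?**

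- *1F and 1G maintenance.* The infusion continues while it is reduced, so there is a period below 130 mmHg with treatment still running. As an illustration, assume the taper goes from the maximum to the starting rate, with one interval per reduction. Clevidipine 32→16→8→4→2 mg/hour is four reductions: 4 × 2 = 8 to 4 × 10 = 40 minutes. Nicardipine 15→12.5→10→7.5→5 mg/hour is also four: 4 × 2 = 8 to 4 × 15 = 60 minutes. The tables do not say where a taper ends, and lower starting rates shorten it. Table 4 lists both hypotension and tachycardia for each of these drugs.
- *1C and 1D maintenance.* The drug is stopped outright, and the bullet follows at once. For urapidil Table 4 lists palpitations and orthostatic hypotension; for phentolamine it lists tachycardia but no hypotension.
- *1C and 1D initial.* Pushes of the named drug end at target SBP (below 140 mmHg in 1C, 130-140 mmHg in 1D), and every later add-on needs BP persistently above 140 mmHg. The rows have no stop at 130 mmHg, so the bullet conflicts only with section 6.1.1, and only if SBP overshoots below 130.

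**6. Is precedence stated?** Neither section 6.1.1 nor any of the four appendices says which instruction wins.

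**The case against.** The best defence is that section 6.1.1 already settles the matter. If the beta blocker is a BP-lowering drug, the arm-wide threshold forbids starting it below 130 mmHg; if it is given for rate control, it does not contradict a stop on BP lowering. The first half is a sensible reading, and it is a main reason why the point is minor. It does not remove the defect, because a table used at the bedside should not need the reader to choose between two readings of a safety stop.

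A second argument is that adding a drug presupposes a running regimen, and in 1C and 1D maintenance the regimen has just been stopped. That has force, and it is why 1F and 1G are the clearer cases. It is still an inference: the bullet does not say that it lapses on cessation, and Table 4 gives urapidil a duration of 3-4 hours, so its effects can outlast the order to stop.

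Third, sections 6 and 6.1.1 let clinicians modify treatment, and section 7 allows it in the patient's interest. This lowers the hazard but sets no precedence.

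A reader might go further and treat all six places as equally contradictory. The documents do not support that: in the two initial rows escalation ends at target, before 130 mmHg is reached. A reader might also take Table 4 to predict the overlap for all four drugs. It pairs plain hypotension with tachycardia only for clevidipine and nicardipine. The urapidil entry is orthostatic, whereas section 8 has trial BP measured supine.

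**Conclusion.** The defect is real and minor. In four of seven maintenance tables, two neighbouring bullets give opposing orders when SBP is below 130 mmHg and the heart-rate trigger is met, and the second also conflicts with section 6.1.1. The case is strongest in 1F and 1G, weaker in 1C and 1D maintenance, and weakest in the two initial rows.

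This rests on reading the bullet as written and on the protocol's own use of beta blockers as BP-lowering agents. The documents give neither the frequency of the overlap nor the number of patients treated under each appendix, so no patient count can be stated. It would be wrong to infer that patients were harmed or that the treatment comparison is biased; nothing in the protocol or SAP shows either. Endpoints, power and analysis are unaffected.

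**What to change.** In all six places, put a systolic condition in front of the bullet: *If SBP is at least 130 mmHg, and HR has risen by more than 15 bpm or is above 90 bpm, add an IV beta blocker.* Alternatively, state in the four appendices that the section 6.1.1 cessation rule at SBP <130 mmHg overrides the heart-rate bullet.

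The cost is one clause in six rows of four tables, a minor amendment with ethics notification (which section 4.1 assigns to each site's principal investigator), and a memo to sites. The number of sites using these appendices is not given. No extra patients, visits or data are needed.

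The benefit is limited to patients still to be treated and to any reuse of the tables. The SAP describes Arm B as concluding and gives August 2018 for final follow-up.

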## Appendix 1D - BP protocol for centres with Phentolamine (China)

Early intensive BP lowering group	TREATMENT PROTOCOL
INITIAL therapy	
BP Target	SBP 130-140 mmHg reached within 60 minutes of Randomisation into the BP arm
Monitoring	
 
• Continuous HR monitoring
 
• Record BP/HR q 5 mins during active treatment, then q 15 min for first hour, q 30 min for next 5 hours and then hourly to 24 h
 

Phentolamine (IV)	
 
• Phentolamine test dose: 2.5 mg IV bolus over 1 minute
 
• If SBP > 140 mmHg and HR >55 bpm, repeat 2.5 mg bolus in 5 minutes
 
• 5 mg IV push q 5 mins until target SBP reached (130-140mmHg) or HR <55 bpm
 
• If HR increases by >15 bpm or is >90 bpm, add IV beta blocker
 

Hydralazine (IV)	If BP persistently >140 mmHg: 
 
• ADD Hydralazine with a test dose: 5 mg IV bolus over 1 minute
 
• If SBP > 140 mmHg, repeat 5 mg IV bolus in 5 minutes
 
• If SBP still >140mmHg, give 10 mg IV bolus q 5 mins until target SBP reached. Increase to 20 mg bolus if required
 
• Maximum hydralazine dose = 240mg/24 hours
 

Glyceryl Trinitrate (Topical)	If BP persistently >140 mmHg: 
 
• ADD topical glyceryl trinitrate (paste or patch) at a rate of 5-10 mg/24hour (≈200-400 µg/hour). NB: also known as topical nitroglycerin
 

Continuous IV Infusions (requires ICU admission)	If BP persistently >140 mmHg: 
 
• Phentolamine infusion 0.2-5 mg/minute
 
• If target still not reached, ADD infusion of hydralazine 50-150 µg/min OR glyceryl trinitrate 1-100 µg /min
 

MAINTENANCE therapy	
BP Target	Maintenance of SBP 130-140 mmHg
Monitoring	Once SBP is under target (confirmed by 4 readings 15 minutes apart): 
 
• Record BP/HR q 30 minutes for 5 hours and then q 1 h for 18 h.
 

IV treatment prn	If SBP exceeds 140mmHg at any point: 
 
• Give Phentolamine (5 mg) and/or hydralazine (10-20 mg) boluses. BP and HR should then be recorded 5 and 15 minutes later
 
• If SBP is <140mmHg, Phentolamine 5 mg (dose dependent on initial response) should be administered q 6 hours for the first 24 hours after symptom onset (total of 3 doses)
 
• If SBP < 130 mmHg or HR <55 bpm, then cease treatment
 
• If HR increases by >15 bpm or is >90 bpm, add IV beta
 

	
blocker
 
 
Note: phentolamine and hydralazine may be used together during the maintenance phase
 

Oral treatment	
Start treatment by 24 hours (use nasogastric if required)
 
 
If not contraindicated and no other drug is specifically indicated, start combination therapy of ACEI + diuretics in addition to previous anti-hypertensives
 

**Note: Monoamine oxidase inhibitors are not recommended with this BP lowering agent and phosphodiesterase inhibitors must not be used with GTN.**

**Key to abbreviations:** ACEI – Angiotensin converting enzyme inhibitor; BP – blood pressure; bpm – beats per minute; HR – heart rate; ICU – intensive care unit; q – every; prn – as required;  $\mu\text{g}/\text{Kg}/\text{min}$  – micrograms per kilogram per minute;  $\mu\text{g}/\text{min}$  – micrograms per minute.

